12.2 Planned Interim Analyses (if applicable)

No interim analysis is currently planned. If an interim analysis is conducted, it will be described in the SAP which will be finalized before any unblinding of treatment groups occurs.

12.3 Analysis Sets

The following analysis sets will be used in the statistical analyses.

All Enrolled (ENR) Set: The ENR Set will contain all patients who signed the informed consent or the study.

All Patients Randomized (RND) Set: The RND Set will contain all patients who signed the informed consent and were randomized to study medication. Patients will be classified according to randomized treatment. Intent-to-treat (ITT) Set: The ITT Set will contain all randomized patients who received at least 1 dose of study drug and who had a valid (pre-dose) baseline assessment and at least 1 valid post-baseline assessment of MADRS. Patients will be classified according to randomized treatment, regardless of the treatment received during the course of the study.

Per-protocol (PP) Set: The PP Set will contain all ITT patients who do not have any major protocol deviations. The major protocol deviation criteria will be specified in the SAP and finalized as part of the blinded data review prior to the final database lock. Patients will be classified according to treatment actually received.

Safety Analysis Set: The Safety Analysis Set will contain all patients who received at least 1 dose of study drug. Patients will be classified according to treatment actually received.

Pharmacokinetic (PK) Set: The PK Set will contain all patients who received at least one dose of study medication and had at least 1 PK sample collected and analyzed and for whom at least one valid assay result (according to laboratory guidelines) has been obtained. Protocol deviations (e.g., dosing errors) and certain AEs (e.g., emesis) will be considered when assigning patients to the PK set. Patients with partial data will be evaluated on a case-by-case basis to determine if sufficient data are available for meaningful analyses.

Unless otherwise specified, the ITT and PP Sets will be used for analysis of efficacy endpoints and the Safety Analysis Set will be used for analysis of safety endpoints.

12.4 Statistical Analysis Methodology

Categorical variables (e.g., AEs) will be summarized using the number and percentage of patients in specified categories. Unless otherwise stated, the calculation of percentages will be based on the number of patients in the analysis set of interest. Continuous variables (e.g., MADRS score) will be summarized using descriptive statistics including number of patients, mean, standard deviation, median, minimum, and maximum.

Source data for summary tables and statistical analyses will be presented as patient data listings.

First treatment with study medication and baseline assessments are scheduled for Visit 2 on Day 1. For analysis purposes, baseline is defined as the last non-missing measurement before the first treatment with study medication. Assessments on Day 1 for which time are recorded will be considered baseline if the assessment time is before the time of the first treatment with study medication. Assessments on Day 1 for which

the time is missing, and are, according to the study Schedule of Events, supposed to be collected prior to treatment (pre-dose), will be considered baseline.

Safety, efficacy, and quality of life data will be listed for all treated patients and summarized by treatment group and time point (visit and relative study day), unless stated otherwise in the SAP. All total and subscale scores will be derived from available individual items. In case of missing items, the total and subscale scores will be considered missing. Plasma concentrations below the limit of quantification (BLQ) will be flagged in the data listings and will be set to zero in the calculation of summary statistics of concentration values and derivations of PK parameters.

Unless stated otherwise, statistical tests will be performed at a 2-sided significance level of 0.05, leading to 95% (2-sided) confidence intervals (CIs).

All investigative sites with fewer than a prespecified number of patients who received ITI-007, as detailed in the SAP, will be pooled together and considered a single site for analysis as follows: the largest site with fewer than the prespecified number of ITI-007 patients will be pooled with the smallest site with fewer than the prespecified number of ITI-007 patients within the same country or geographic region. If this results in a pooled site still having fewer than the prespecified number of ITI-007 patients, this site will be pooled together with the next smallest investigative site within the same country or geographic region, if one exists; otherwise, no further pooling is needed. If the primary efficacy analysis model presents convergence issues due to the too small number of patients per site, including pooled site, the same site pooling algorithm will be applied again, but this time pooling sites with a larger prespecified number of ITI-007 patients per sites, as determined based on the primary efficacy variable, will be used for any analysis model that includes site as a fixed effect. The actual investigative site numbers will be included in the listings.

All statistical analysis will be performed using SAS® software Version 9.4 or higher.

Additional details regarding the statistical analysis methodology will be provided in the SAP.

12.4.1 Patient Disposition, Analysis of Demographics and Other Baseline Characteristics

Patient disposition will be summarized by treatment group, when applicable, and overall, including incidence of screening failure and incidence of treatment or study discontinuation and the corresponding reasons. The number and percentage of randomized patients who discontinued due to an AE associated with worsening of

bipolar depression will be summarized. Similarly, the number and percentage of randomized patients who discontinued due to an AE not associated with worsening of bipolar depression will also be presented. Time to discontinuation due to all reasons, AEs (all, AEs associated with worsening of bipolar depression, and AEs not associated with bipolar depression), lack of efficacy, or due to any reason of special interest will be evaluated using the Kaplan-Meier method, where patients who complete the On-treatment Period or who discontinue for a reason other than the one being evaluated, will be censored. The Log-rank test will be used to compare the time to discontinuation between the treatment groups.

Demographic and baseline characteristics, including Bipolar Disorder diagnosis and baseline efficacy parameters, will be listed and summarized by treatment group. No inferential statistics will be presented.

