	Patients will self-administer doses orally, once daily, at home, each evening, for the duration of the double-blind On-treatment Period. Treatments will be provided in dose cards containing over-encapsulated tablets, and patients will be instructed to take 1 tablet per dose.
Study Duration:	Approximately 18 months from first patient screened or 17 months from first patient randomized until data analysis is completed, assuming an approximate 13-month enrollment period depending on clinic and patient availability, plus two months to complete clinical conduct and an additional two months to complete data analysis.
Patient Participation Duration:	For each patient completing the study, the study will last a maximum of approximately 10-12 weeks (9 visits), including screening, the on-study treatment period, and the safety follow up.

Estimated Time to	Approximately 13 months is anticipated from first patient
Complete	randomized to last patient randomized, depending on clinic
Enrollment:	and patient availability.

StatisticalA formal and detailed statistical analysis plan (SAP) will beMethods:finalized prior to unblinding the patients' treatment
assignments.

Analysis of the Primary and Key Secondary Efficacy Endpoints

The treatment effect on the primary efficacy endpoint will be evaluated using a mixed model repeated measures (MMRM) method. The model will include the change from baseline at each pre-specified time point in the MADRS total score as the response variable, visit, treatment group, site (or pooled site), and the Bipolar Disorder stratification variable (Bipolar I and Bipolar II) as factors, the baseline MADRS total score as a covariate and interaction terms for treatment group-by-visit, and visit-by-baseline MADRS total score.

The Key Secondary Efficacy Endpoint will be analyzed using the MMRM method, similar to the one specified for the analysis of the primary efficacy endpoint, while substituting MADRS total score related variables in the MMRM with the corresponding CGI-BP-S related ones, such as baseline score and visit-by-baseline score interaction.

Safety Analyses

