5.4.1 Randomization Procedures

An interactive voice response system (IVRS)/interactive web response system (IWRS) (English only) will be used to administer the randomization schedule. Unblinded biostatistics personnel not participating in the conduct of the study will generate a permuted block randomization schedule using SAS software Version 9.2 or later for IVRS/IWRS, which will link sequential patient randomization numbers to treatment codes. In the event that the blind needs to be broken because of a medical emergency, the investigator may unblind an individual patient's treatment allocation (Section 5.4.3). The randomization schedule will be stratified by Bipolar I or Bipolar II diagnoses at screening.

Each patient will be assigned a randomization number, at the time of randomization, which will be separate from the patient identification number. Once a randomization number has been allocated to a patient, it may not be assigned to another patient.

The IVRS/IWRS will send visit notifications to the study site personnel, confirming the patient data that were entered. The IVRS/IWRS notifications should be filed securely at the study site.

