12.1 Sample Size Considerations

Approximately 350 patients will be randomly assigned in a 1:1 ratio to 1 of the 2 treatment arms (60 mg ITI-07 or placebo). A sample size of 350 patients randomized, which will provide approximately 326 evaluable patients (approximately 163/treatment group) assuming a 10% early discontinuation rate before the first post-dose assessment in the primary efficacy outcome measure (MADRS), will provide 85% power to detect a clinically relevant treatment difference from placebo of 3 points on the MADRS total score with ITI-007, with a common standard deviation of 9.0at an overall 2-sided significance level of 0.05.

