The number and percentage of randomized subjects who discontinued due to an adverse event associated with worsening of bipolar depression will be summarized. The number and percentage of randomized subjects discontinued due to an adverse event not associated with worsening of bipolar depression will also be presented.

...\ITI\ITI-007\MYA11638\Biostatistics\Documentation\SAP\ITI-007-404 SAP Final V1.0 12JUN2019.docx Document: Author:

Version Number:1.0

INTRA-CELLULAR THERAPIES INC. (ITCI)

STATISTICAL ANALYSIS PLAN: PROTOCOL ITI-007-404

Page 19 of 53

The time to treatment discontinuation due to all reasons, adverse events, lack of efficacy, or due to any other reason of special interest will be evaluated separately using the Kaplan-Meier method. Time to treatment discontinuation of subjects in the SAF Set will be defined as the date of discontinuation minus date of first dose of study medication plus 1. Subjects who complete treatment or who discontinue for a reason other than the one being evaluated will be censored. The Log-rank test will be used to compare the time to treatment discontinuation between the 60 mg ITI-007 treatment group and placebo group. The same analysis will be repeated for time to treatment discontinuation for any reason, where only subjects who complete the 6-week Treatment Period will be censored.

The number and percentage of subjects who withdrew from the study will be summarized by visit, treatment group and overall for all subjects in the RND Set. The number of subjects randomized will also be summarized by site for the RND Set. The number of subjects remaining on treatment over time will be presented in a figure.

| The number and percentage of subjects in the RND set. | f subjects in the SAF set, the ITT set will be summarized by treatment group and overall for all |
|---|--|
| | |
| | |
| | |
| | |
| | |
| | |
| | |

Document: Author: ...\ITI\ITI-007\MYA11638\Biostatistics\Documentation\SAP\ITI-007-404 SAP Final V1.0 12JUN2019.docx Version Number:1.0

11. Demographic and other Baseline Characteristics

Demographic data and other baseline characteristics will be presented for the ITT and SAF Sets.

No formal statistical testing will be carried out for comparing demographic or other baseline characteristics between the two treatment groups.

The following demographic and other baseline characteristics will be reported:

Demographics

- o Gender
- Age (years) calculated as (Date of Informed Consent Date of Birth)/365.25

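### The log-rank tests of time to discontinuation omit the Bipolar I/II randomization stratum; if dropout differs by diagnosis, they are slightly conservative and lose a little power

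*Protocol*

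**What the plan says.** Protocol section 5.4.1 sets the design: "The randomization schedule will be stratified by Bipolar I or Bipolar II diagnoses at screening". The primary MMRM, in the statistical methods of the Protocol Summary, carries the stratum with "site (or pooled site), and the Bipolar Disorder stratification variable (Bipolar I and Bipolar II) as factors". SAP sections 15.1.3 and 15.2 repeat it for the primary and key secondary models. SAP section 16.4 includes it in the vital-sign MMRM and also in the exploratory LOCF ANCOVA.

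Time to discontinuation is handled differently. Protocol section 12.4.1 plans Kaplan-Meier estimates for all reasons, adverse events, lack of efficacy and other reasons of interest, under the rule that "patients who complete the On-treatment Period or who discontinue for a reason other than the one being evaluated, will be censored". The test is then given as "The Log-rank test will be used to compare the time to discontinuation between the treatment groups". SAP section 9 has "The Log-rank test will be used to compare the time to treatment discontinuation between the 60 mg ITI-007 treatment group and placebo group". Both sentences are complete in the public text, and neither mentions a stratum. The default in Protocol section 12.4 applies: "Unless stated otherwise, statistical tests will be performed at a 2-sided significance level of 0.05".

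**The concern.** Stratified randomization balances the two diagnoses across the arms. If diagnosis predicts dropout, that balance removes some chance variation from the comparison between arms. An unstratified log-rank test does not take account of this. Its variance estimate is then too large, its true type I error falls below 5%, and it detects a real difference slightly less often than the design allows.

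For an efficacy claim, conservatism is the safe side. For a comparison of who stops treatment and why, the error of interest is missing a real difference between the arms, so a little sensitivity is given away for nothing. The plan gives no reason for adjusting exploratory vital-sign models for the stratum and leaving these tests without it.

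**Working it through.** **The plan's own figure.** The only power statement concerns MADRS: about 163 evaluable patients per group, a difference of 3 and an SD of 9.0 (Protocol section 12.1). Power = Φ(3 / (9 × √(2/163)) − 1.96) = Φ(3.009 − 1.960) = Φ(1.049) = 85.3%, which agrees with the stated 85%. No power, event count or hazard ratio is stated for the log-rank tests, so there is no plan figure to reproduce for them.

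**Inputs from the documents.** N = 350, allocation 1:1, two strata, 42 days on treatment, two-sided 0.05.

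**Assumed inputs.** Bipolar II share 20% to 50%; placebo dropout by diagnosis as listed below; hazard ratio 1.8 for active versus placebo. The documents' only dropout figure is an overall 10% before the first post-dose MADRS, which is neither by diagnosis nor for the full six weeks.

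**When the effect exists.** For moderate event rates the log-rank test behaves much like a comparison of proportions. Let w be the Bipolar II share, p_I and p_II the dropout proportions, and p̄ their weighted mean. Under no treatment effect:

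- The unstratified test uses a variance proportional to p̄(1 − p̄).
- With balance within strata, the true variance is proportional to p̄(1 − p̄) − w(1 − w)(p_II − p_I)².
- The ratio is R = 1 − w(1 − w)(p_II − p_I)² / [p̄(1 − p̄)], and the true type I error is 2[1 − Φ(1.96/√R)].

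R equals 1 exactly when p_I = p_II, so the conservatism is conditional. Examples at w = 0.2:

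- 15% vs 30%: p̄ = 0.18; R = 1 − 0.0036/0.1476 = 0.976; type I error 4.7%.
- 10% vs 30%: p̄ = 0.14; R = 1 − 0.0064/0.1204 = 0.947; type I error 4.4%.
- 3% vs 6%: p̄ = 0.036; R = 1 − 0.000144/0.034704 = 0.996; type I error 4.95%.

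Simulated type I error agrees: 4.7% at 15% vs 30%, and 4.55% at 10% vs 30%.

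**Power.** Simulated with exponential dropout over 42 days, 1:1 within stratum, hazard ratio 1.8, and 6,000 to 8,000 runs per row. Both tests were applied to the same simulated data.

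| Placebo dropout, Bipolar I / II | Bipolar II share | Unstratified | Stratified | Gain (points) |
|---|---|---|---|---|
| 15% / 15% | 50% | 68.6% | 68.6% | 0.0 |
| 10% / 20% | 20% | 57.8% | 58.4% | 0.6 |
| 10% / 20% | 40% | 64.7% | 65.8% | 1.1 |
| 15% / 30% | 50% | 83.0% | 84.1% | 1.1 |
| 10% / 30% | 20% | 62.4% | 65.7% | 3.3 |
| 10% / 30% | 40% | 72.1% | 75.3% | 3.2 |
| 3% / 6% | 20% | 21.1% | 21.3% | 0.2 |
| 5% / 10% | 40% | 37.7% | 38.2% | 0.5 |
| 2% / 6% | 40% | 21.1% | 21.7% | 0.6 |

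With a Bipolar II share of 20% to 40%, the gain is 0.6 to 1.7 points at 15% vs 30% and 0.1 to 0.7 points at 15% vs 25%. The last three table rows represent single-reason discontinuation, which is necessarily rarer than discontinuation for any reason. A fourfold difference would cost more (10% vs 40%, even split: 82.0% against 87.0%), but nothing in the documents points to one.

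**The case against.** The case for leaving the plan alone is reasonable, and most of it stands.

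- These are disposition comparisons. Protocol section 12.4.4 names only MADRS and CGI-BP-S as primary and key secondary endpoints. The discontinuation tests have no power statement, and no visible text makes a decision depend on their p-values.
- An unstratified log-rank test is valid and common in a disposition table. Its error here is on the conservative side.
- The SAP's other simple between-arm safety test, the chi-square test for TEAEs in section 16.1.1, is also unstratified. The contrast is therefore between adjusted models and unadjusted simple tests, and the log-rank test is not a lone exception.
- The size depends wholly on assumed inputs, and for single-reason tests the gain is negligible.

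What this does not answer is that stratifying has no practical downside. With two strata and about 350 patients, nothing measurable is lost when dropout is equal, and the test then follows the randomization.

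A reader might also infer that a blunted dropout comparison weakens the missing-at-random basis of the primary analysis. The documents do not support that. Missing at random, as SAP section 7.1 describes it, concerns unobserved outcomes given the observed data. A log-rank p-value on dropout by arm neither establishes nor refutes it. SAP section 15.1.2 assigns that question to sensitivity analyses, and dropout by arm, reason and time is tabulated in any case.

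**Conclusion.** The omission is real but minor. If dropout differs between Bipolar I and Bipolar II, the planned tests are slightly conservative and slightly underpowered relative to a stratified version. With N = 350 and an assumed hazard ratio of 1.8, the cost is about 0 to 2 points of power for up to a twofold difference in all-reason dropout. It is about 3 points at 10% vs 30%, well under 1 point for low-frequency single reasons, and none if dropout is equal.

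Two stronger readings should be resisted. The tests are not conservative as such: without a difference by diagnosis they have the correct size. Nor is 3 points the expected loss, because it needs a threefold difference that no figure in the documents suggests. No primary or key secondary conclusion changes.

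**What to change.** In SAP section 9, before unblinding, replace the test with *a log-rank test stratified by the randomization stratum (Bipolar I or Bipolar II)*. Use the same screening stratification variable as the MMRMs. The all-reason test is where it can matter; apply it to the reason-specific tests for consistency. The Kaplan-Meier displays can stay as planned.

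The cost is one phrase and one stratum term in the program. Protocol section 12 allows such changes to be recorded in the SAP without a protocol amendment, so section 12.4.1 can be aligned if the protocol is amended for another reason.

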12.4.2 Prior and Concomitant Medications

Prior, prior concomitant, concomitant, and post-treatment medications, defined by start and stop dates relative to study medication administration, will be summarized by preferred term and treatment group. Patients with multiple occurrences of a medication in the same preferred term will only be counted once within the preferred term.

During the study, a patient may be treated with zolpidem as described in Section 6.6. The number and percent of patients in the ITT Set receiving zolpidem and the total number of days on zolpidem will be summarized by treatment group for the Screening Period, for each week during the On-treatment Period and for post-treatment with ITI-007.

12.4.3 Study Medication Exposure and Treatment Compliance

Exposure to study medication and treatment compliance will be presented using the ITT and Safety Analysis Sets. Duration of exposure (days) and dosing compliance (%) will be calculated and summarized by treatment group. Additionally, the number and percentage of patients exposed to study medication will be presented by study week, defined by the planned visits.

12.4.4 Analysis of Primary and Key Secondary Efficacy Endpoints

The study is designed to evaluate the efficacy profile of ITI-007 60 mg based on the following primary and key secondary efficacy endpoints:

- Primary Endpoint Change from baseline to Day 43 in the MADRS total score.
- Key Secondary Endpoint Change from baseline to Day 43 in the CGI-BP-S score.

Safety Analyses

All safety parameters will be summarized using the safety analysis set.

Safety data such as reported and observed AEs, treatment emergent AEs (TEAEs) and SAEs, clinical laboratory results, vital signs, physical examinations and neurological findings, ECGs, and the different rating scales (YMRS, C-SSRS, AIMS, BARS, and SAS) will be summarized by treatment group and visit. When appropriate, out-of-range values

will be flagged in data listings and tabulated. Shift tables will be prepared for pre-specified safety measures, such as laboratory parameters, ECG and weight. Parameters collected in duplicate or triplicate will be analyzed as an average of the measures for the relevant time point, including baseline.

Reported AE terms will be coded using the latest version of the Medical Dictionary for Regulatory Activities (MedDRA). Treatment-emergent adverse events (TEAEs) will be defined as any AEs, regardless of the relationship to study drug, that occur or worsen in intensity after the first dose of study drug and on or before the date of last dose of study drug plus one day. Treatment-related TEAEs will be defined as any TEAEs that are considered by the investigator to be either possibly, probably, or definitely related to study drug. If relationship to study drug is missing, the TEAE will be considered as treatmentrelated. Severity of TEAEs will also be determined by the Investigator. All TEAEs, treatment-related TEAEs, and serious TEAEs will be summarized by treatment group, primary system organ class categories, and preferred terms. If a patient reports the same TEAE more than once within the same system organ class and preferred term, the event with the worst-case relationship to study drug will be used in the corresponding relationship summaries. Similarly, if a patient reports a TEAE more than once within the same system organ class and preferred term, the event with the worst case severity will be used in the corresponding severity summaries.

Patients who discontinue study or study drug due to AEs will be listed and summarized by system organ class and preferred term. TEAEs will be categorized to monitor signals of potential abuse of ITI-007 and the number and percentage of patients with at least one abuse-related TEAE will be summarized by the pre-specified categories.

Additional summaries of TEAEs will be presented as deemed necessary and will be specified in the SAP.

Laboratory assessments, including hematology and chemistry, vital signs and ECGs, will be listed and summarized by treatment group and visit. Summaries may include actual and change from baseline, incidence of abnormal values according to normal range criteria, shift from baseline to each visit according to markedly abnormal criteria, and listing of patients meeting certain abnormal criteria. Pre -specified chemistry results, including but not limited to blood levels of fasting glucose, total cholesterol, triglycerides, and insulin will be evaluated for whether there is a difference between ITI-007 and placebo. Any comparison between the treatment groups will be considered exploratory.

The observed and change from baseline in the scores of the different rating scales (YMRS, C SSRS, AIMS, BARS, and SAS) will be summarized by treatment group and visit.

Additional details for analyses on safety assessments will be provided in the SAP.

